15.6.5. Pharmacokinetic

This document is intended for planning analysis of PK concentration data only. Population pharmacokinetics and identification of important determinants of variability will be described in a separate document.

Pharmacokinetic Analyses		
Plasma CAB and RPV Concentration-time Data		
Plasma samples for determination of CAB and RPV concentration will be collected throughout the Maintenance Phase and at the withdrawal visit. Additional samples will be collected for storage during the Long-Term Follow-Up Phase.		
Evaluable Concentration		
PK concentration will be summarized in two ways: 'all data' without regard to timing relative to scheduled time and 'evaluable data'.		
The 'evaluable data' are from the samples that met sample collection window criteria. Sampling windows are set relative to the previous dose as follows:		

 • 20-28 hrs after last oral dose taken and properly administered last 3 oral doses for pre-dose sample at Week 4B for participants requiring oral lead-in • ± 4 days for pre-dose sample at visits other than Week 4B, and for pre-dose samples at Week 4B for participants not requiring oral lead-in (e.g. participants transitioning from ATLAS Q4W and remain on Q4W arm in this study) • 3-10 days post last injection for 1-week post injection visits; • Samples impacted by dosing errors (wrong dose) or oral bridging will also be excluded 		
Timepoint	Evaluable Window	For Programming:
Pre-dose: WK4B for participants requiring oral lead-in	20-28 hrs after last oral dose taken and the last 3 oral doses administered properly	$20 \text{ hrs} \leq \text{Time since Last Oral Dose} \leq 28 \text{ hrs}$ and the last 3 oral doses administered on the three consecutive days prior to WK4B.
Pre-dose at other visits, Pre-dose WK4B for participants not requiring oral lead-in	± 4 days	For Q4W arm, Day 1 pre-dose, and Week 8 for those transitioning from SOC (i.e. requiring oral lead-in) on Q8W arm: $24 \text{ days} \leq \text{Days Since Last Injection} \leq 32 \text{ days}$ For visits other than above on Q8W arm: $52 \text{ days} \leq \text{Days Since Last Injection} \leq 60 \text{ days}$
1-WK-Post:	3-10 days post last injection	$3 \text{ days} \leq \text{Days Since Last Injection} \leq 10 \text{ days}$
Relative Time is calculated relative to the date and time of last previous dose. For example, if the time of the last previous dose (e.g. oral lead-in/oral-bridging) is missing, then the relative time for		

Pharmacokinetic Analyses

pre-dose PK sample will be set to missing and the sample will not be considered 'evaluable'.

If a pre-dose sample is collected on the same day as the first dose of oral bridging, the time of the first dose (not recorded in eCRF) is assumed to be 'after' the collection of pre-dose sample, unless medical monitor or Data querying informs otherwise.

The time-deviation (hours) from the targeted timepoint will be calculated for the samples '1-Week-POST' only using the following formula:

$$\text{Time_deviation (hrs) for '1-Week-POST'} = \text{Sample date.time} - \text{last previous injection date.time} - 7 * 24 \text{ hours}$$

The following windows are for defining 'evaluable' Long-term Follow-up phase PK concentrations.

Timepoint	Evaluable Window	For Programming:
LTFU MONTH 1/WD	± 4 days	24 days ≤ Days Since Last Injection ≤ 32 days
LTFU MONTH 3	± 1 Weeks	77 days ≤ Days Since Last Injection ≤ 91 days
LTFU MONTH 6	± 2 Weeks	154 days ≤ Days Since Last Injection ≤ 182 days
LTFU MONTH 9	± 2 Weeks	238 days ≤ Days Since Last Injection ≤ 266 days
LTFU MONTH 12	± 2 Weeks	322 days ≤ Days Since Last Injection ≤ 350 days

15.6.6. Health Outcomes

HIVTSQs

Questionnaire (Questions 1-12 are scored)

CCI - This section contained Clinical Outcome Assessment data collection questionnaires or indices, which are protected by third party copyright laws and therefore have been excluded.

CCI
Total Treatment Satisfaction Score

 • Total Treatment Satisfaction Score is computed with items 1-11. Items 1-11 are summed to produce a score with a possible range of [redacted] to [redacted]. • Item 12 will not be included in Total Treatment Satisfaction Score. Instead, it will be treated as a stand-alone item only. • Higher scores represent greater treatment satisfaction as compared to the past few weeks. • A maximum of 5 items can be missing, which can be imputed to reflect the mean of the completed item scores. If 6 or more items are missing, then the treatment satisfaction scale score should not be computed and instead be imputed using LOCF.
Individual Item Scores

 • Items are rated as [redacted] (CCI [redacted] etc.) to [redacted] (CCI [redacted] etc.). • Higher scores represent greater satisfaction with each aspect of treatment 
 • For individual item scores outputs, missing scores will not be computed (according to Page 7 of the [HIVTSQ User Guidelines, 2016]) and instead be imputed using LOCF.
HIVTSQc
Questionnaire (Questions 1-12 are scored [redacted] to [redacted])

CCI - This section contained Clinical Outcome Assessment data collection questionnaires or indices, which are protected by third party copyright laws and therefore have been excluded.

Total Treatment Satisfaction Score (change)

 • Total Treatment Satisfaction Score is computed with items 1-11. Items 1-11 are summed to produce a score with a possible range of [redacted] to [redacted]. • Item 12 will be computed as an individual item only. • The higher the score, the greater the improvement in satisfaction with treatment; the lower the score, the greater the deterioration in satisfaction with treatment. A score of [redacted] represents [redacted]. • A maximum of 5 items can be missing, the missing scores will be imputed with the mean of the completed item scores. If 6 or more items are missing, then the overall treatment satisfaction scale score should not be computed and will remain missing.

Individual Treatment Satisfaction Change Item Scores

- Items are rated as CCI (CCI [redacted] etc.) to CCI (CCI [redacted] etc.).
- The higher the score, the greater the improvement in satisfaction with each aspect of treatment and the lower the score, the greater the deterioration in satisfaction with each aspect of treatment.

Questionnaire Version

- Three versions of the HIVTSQc questionnaire are available with the questions the same and only the overhead text is different.
 - Q4W ATLAS to Q4W ATLAS-2M: for participants who randomized to Q4W arm in ATLAS and then randomized to Q4W arm in ATLAS-2M
 - Q4W ATLAS to Q8W ATLAS-2M: for participants who randomized to Q4W arm in ATLAS and then randomized to Q8W arm in ATLAS-2M
 - SOC to Q4W or Q8W ATLAS-2M: for participants who either were randomized to SOC arm in ATLAS or did not participate in ATLAS
- If a participant takes a wrong version of the questionnaire, the data collected from the wrong version will be considered invalid and will not be included in the summary.

PIN

Questionnaire (Each question is scored CCI)

CCI - This section contained Clinical Outcome Assessment data collection questionnaires or indices, which are protected by third party copyright laws and therefore have been excluded.

CCI - This section contained Clinical Outcome Assessment data collection questionnaires or indices, which are protected by third party copyright laws and therefore have been excluded.

Dimension Score (Chevat et al, 2008)

- Domains and Clusters
 - CCI [redacted] items [CCI]
 - CCI [redacted] items [CCI]
 - CCI [redacted] items [CCI]
 - CCI [redacted] items [CCI]
- 5 items not included in any of these domains and maintained as individual items (items [CCI])
- No overall score is calculated per the guidance
- The score of a domain is calculated as the mean of all items with the domain. Higher scores represent worse perception of injection.
- A maximum of <50% items can be missing within a domain, which can be imputed to reflect the mean of the completed item scores within the domain. Thus, if the number of missing items is ≥ 3 (CCI), ≥ 2 (CCI), ≥ 1 (CCI), then the total score for the domain should not be computed and instead be imputed using LOCF (Section 15.7.2.2)

Individual Item Scores

[figure not shown]
- Items are rated on a 5-point scale, ranging from [CCI] etc.) to [CCI] etc.).
- Lower scores represent worse perception of injection
- For individual item scores outputs, missing scores will not be computed and instead be imputed using LOCF (Section 15.7.2.2).

HAT-QoL (Holmes, 1999)

Questionnaire (Questions 1-14 are scored [CCI] to [CCI])

CCI - This section contained Clinical Outcome Assessment data collection questionnaires or indices, which are protected by third party copyright laws and therefore have been excluded.

[figure not shown]
CCI - This section contained Clinical Outcome Assessment data collection questionnaires or indices, which are protected by third party copyright laws and therefore have been excluded.

Life satisfaction, HIV medications, disclosure worries

- The ratings for Items (a, b, c, d, e) will be recoded as below for analysis:
- | Response option | Life Satisfaction | Medication/disclosure worries |
|-----------------|-------------------|-------------------------------|
|-----------------|-------------------|-------------------------------|

CCI - This section contained Clinical Outcome Assessment data collection questionnaires or indices, which are protected by third party copyright laws and therefore have been excluded.

- A maximum of 50% question items can be missing within a domain, which can be computed and replaced with the mean of the completed item scores within the domain. Thus, if there are more than 1 item missing for Life Satisfaction, and more than 2 items missing for Medication/disclosure worries, then the total score for the domain should not be computed and instead be imputed using LOCF (Section 15.7.2.2). A computed score for missing value will be added to calculate a total score for the domain. Total score for each of the three domains will be calculated and will be denoted as 'LISAT' for life satisfaction, 'MEDWO' for medication worries, and 'DISWO' for disclosure worries.

- Transform each dimension's total imputed value score to the 0-100 scale using the following formulae:

Life satisfaction: CCI [redacted]

Medication worries: CCI [redacted]

Disclosure worries: CCI [redacted]

The higher the score, the greater satisfaction to life and the less worry. The transformed dimension score for each domain will be summarized and analysed.

[figure not shown]
Individual Item Scores

- For individual item scores outputs, missing scores will not be computed and instead be imputed using LOCF (Section 15.7.2.2).

ACCEPT (Acceptance/General Dimension) (Gilet H et al, 2014)

Questionnaire (Questions 1-3 constitute to Acceptance/General Dimension)

CCI - This section contained Clinical Outcome Assessment data collection questionnaires or indices, which are protected by third party copyright laws and therefore have been excluded.

CCI - This section contained Clinical Outcome Assessment data collection questionnaires or indices, which are protected by third party copyright laws and therefore have been excluded.

- Proportion of participants with individual item scores will be calculated.

Individual Item Scores

- Items are rated as C (CCI) to C (CCI) and 'C' with 'CCI'.
- Acceptance/General dimension score is calculated only if at least 2 items in the dimension are completed
- Items will be recoded to score as follows:

Rating	Recode
--------	--------

CCI - This section contained Clinical Outcome Assessment data collection questionnaires or indices, which are protected by third party copyright laws and therefore have been excluded.

- The total score of the dimension is calculated as the mean of the recoded items of the dimension and then linearly transformed to be on a scale from C to C score, as below:

$$\text{Total Score} = \frac{\text{CCI} - \text{C}}{\text{CCI} - \text{C}} \times (\text{CCI} - \text{C}) + \text{C}$$
- For individual item scores outputs, missing scores will not be computed and instead be imputed using LOCF (Section 15.7.2.2).

Preference

Questionnaire

1. Based on your experience which HIV treatment do you prefer?
 - Injectable Long-Acting HIV Treatment every 4 weeks
 - Injectable Long-Acting HIV Treatment every 8 weeks (only select this answer if you received the 8-week injectable regimen of CAB LA + RPV LA during study)
 - Oral daily HIV Treatment
 - No preference

If you selected no preference, skip questions 2 and 3.

If you selected any other response, please continue and complete all questions.

2. What is the main practical attribute of this HIV therapy supporting your preference?
 - Mode of administration
 - Frequency of administration
 - Time required for administration
 - Scheduling visits
 - Storing medications
 - Impact of side effects


  Other, please specify 
3. What is the main benefit related to this HIV therapy supporting your preference?
 
  More convenient, easier to integrate into one's daily life  Less stressful  Less stigma  Easier to take the drug exactly as prescribed  More efficacious  Other, please specify

Questionnaire Version
 
 • Two versions of questionnaire are available. The questions in each version of the questionnaire are the same and only the overhead text is different. 
 ○ ATLAS (from Q4W ATLAS): for participants randomized to Q4W arm in ATLAS. ○ ATLAS-2M (from SOC ATLAS or out): for participants who either were randomized to SOC arm in ATLAS or did not participate in ATLAS.

Data Handling
 
 • Any missing values will remain missing (i.e. no imputation).

Reasons for Continuation/Switch

Questionnaires
 
 • Reasons for Continuation questionnaire is collected for participants who were randomized to Q4W arm in ATLAS. • Reason for Switch questionnaire is collected for participants who either were randomized to SOC arm in ATLAS or did not participate in ATLAS.

Data Handling
 
 • If a participant takes a wrong questionnaire, for example, the participant randomized to SOC arm in ATLAS took Reasons for Continuation questionnaire, the data collected from this wrong version will be considered invalid and will not be included in the summary. • If the questionnaire is taken beyond ± 2 weeks window from maintenance phase treatment start date (i.e. Study Day < -14 or Study Day > 14) will be consider not evaluable and will not be included in the summary. • Any missing values will remain missing (i.e. no imputation).

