4. ANALYSIS POPULATIONS

Population	Definition / Criteria	Analyses Evaluated
Screened	
 • Comprised of all subjects screened for inclusion in the study. • Subjects may be re-screened once, for which they will receive a new subject number. • For disposition displays, except for the listing of subjects who were rescreened, only the latest re-screening data will be included. All screening data will be summarized or listed for other displays. 	
 • Study Population
Randomized	
 • All subjects who were randomly assigned to treatment in the study. • In this study, the randomized population includes all enrolled participants, i.e. the randomized population is equivalent to the enrolled population. • This population will be based on the treatment the participant was randomized to. 	
 • Study Population
Safety	
 • All randomized subjects who received at least one dose of study treatment. • Participants will be assessed according to actual treatment received. 	
 • Safety
Intent-to-Treat Exposed (ITT-E)	
 • All randomized subjects who received at least one dose of study treatment. • Subjects will be assessed according to their randomized treatment, regardless of the treatment they received. 	
 • Study Population • Efficacy • Health Outcomes
Per-Protocol (PP)	
 • All subjects in the ITT-E population with the exception of major protocol violators. • Protocol deviations that would exclude participants from the PP population are defined in Section 4.1 (Protocol Deviations) and Appendix 1: Protocol Deviation Management and Definitions for Per Protocol Population. 	
 • Efficacy (Sensitivity Analysis)

Population	Definition / Criteria	Analyses Evaluated
Pharmacokinetic (PK)	
 All subjects who received CAB and / or RPV and underwent PK sampling during the study and provide at least 1 non-missing CAB and / or RPV plasma concentration value (Non-quantifiable [NQ] values will be considered as non-missing values). 	
 PK

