- t. Participants switching to CAB LA + RPV LA will take final dose of oral lead-in regimen in the clinic at the Week 4B visit and begin injections. If possible, injections should be spaced approximately 2 cm from one another and from the site of any previous injection and or any injection site reaction. Bring RPV LA to approximately room temperature prior to injecting. Time and location of injection (right or left) as well as needle length used will be collected in the eCRF. The first injection can be performed as soon as central lab results become available and safety parameters are reviewed.
- u. All Patient Report Questionnaires/Surveys will be administered via paper instrument at the beginning of the visit before any other assessments are conducted and prior to administration of the eC-CSSRS. Conduct questionnaires/surveys upon Withdrawal only if occurring at or prior to Week 48
- v. The HIVTSQc is to be administered to all participants transitioning from ATLAS and new participants transitioning from oral SOC. For participants transitioning from ATLAS, the version of the HIV-TSQc instrument to be administered will be based on the initial randomization arm at ATLAS Day 1
- w. For patients randomized to oral SOC at Day 1 in ATLAS or new patients on SOC, the reasons for willingness to switch ART will be assessed at Day 1. For patients randomized to CAB LA + RPV LA Q4W in ATLAS, the reasons for willingness to continue long-acting ART in ATLAS-2M will be assessed at Day 1.
- x. Preference Questionnaire will be administered to all participants
- y. Refer to Section 5.5 of the protocol for additional information on performing withdrawal assessments. HIV-1 RNA will be collected as Storage sample only if withdrawal assessments coincide with Week 52 or Week 100 (as per Section 5.5)
- z. Participants receiving one or more injections with CAB LA and/or RPV LA will be assessed with clinic visits at months 3, 6, 9 and 12 during the Long-Term Follow-Up Phase

Note: BP – Blood pressure, HR – Heart Rate, HDL – High Density Lipoprotein, LDL – Low Density Lipoprotein, PT Prothrombin Time, PTT Partial Thromboplastin Time, INR International normalized ratio

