15.3.4. Assessment Window for Health Outcome Data

15.3.4.1. PIN / HAT-QoL / HIVTSQs / HIVTSQc / ACCEPT / Preference

PIN, HAT-QoL, HIVTSQs, HIVTSQc, ACCEPT and Preference questionnaire assessments will be assigned to analysis visits as follows:

1. Baseline will be defined as last available recorded value up to and including the Maintenance treatment start date (expected to be collected at Day 1). Baseline is not applicable for PIN, HIVTSQc and Preference assessments.
2. For post-baseline visits, if the nominal visit identifier as captured in the source dataset corresponds to a scheduled collection per the Time and Events Schedule (see Section 15.2 and [Table 12](#)) and the assessment is collected in the Maintenance Phase (per [Table 14](#)), then the nominal visit identifier will be kept as the analysis visit.
3. For post-baseline visits, if the nominal visit identifier is unscheduled or withdrawal, then the following procedure will be used:
 - a) Assign the assessment to a study phase according to [Table 14](#). Proceed to step b if the assessment is assigned to the Maintenance Phase.
 - b) Identify the ‘last nominal visit’ with the HO assessment performed prior to the unscheduled/withdrawal visit to be slotted.
 - c) The unscheduled/withdrawal visit will be slotted to the planned nominal visit subsequent to the ‘last nominal visit’. If the ‘last nominal visits’ does not exist (e.g. no records originate from a planned nominal visit), then the unscheduled/withdrawal visit will be slot to the first planned nominal visit after Day 1.

Example 1, for HATQoL, the planned nominal visits are Day 1, Week 24, and 48. If a participant has the ‘last nominal visit’ (with HATQoL assessment) at Week 24 prior to withdrawal at Week 36, the withdrawal assessment will be slotted to the subsequent planned nominal visit of Week 48.

Example 2, for HATQoL, if there is unscheduled visit between Week 24 and Week 48. This unscheduled visit will be slotted to Week 48 per the rule. In this case, there are two assessments with analysis visit equal to Week 48 (i.e. the slotted value and the value at

original nominal week 48 visit). The original nominal value will be selected for summary per the rule below for multiple records—see Section 15.3.6.

Table 12 Planned Nominal Visit of Health Outcome Data

Questionnaire	Day 1	Week 8	Week 24	Week 48
PIN		X	X	X
HAT-QoL	X		X	X
HIVTSQs	X		X	X
HIVTSQc				X
ACCEPT	X		X	X
Preference				X

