15.4.3. Study Period

Certain displays will be produced for data collected during the oral lead-in. The study period variable is defined in Table 18 and Table 19. Study period is assigned after the study phase is assigned (screening, maintenance, extension, or long-term follow-up) based on the Tables in Section 15.4.1.

Table 18 Assignment of Study Period for AE Data

Study Period	Date range
Oral Lead-in	
For participants receiving at least one Injection: Maintenance Treatment Start Date \leq Date < Date of First IM Injection
 
For participants withdrawing prior to first Injection: Date \geq Maintenance Treatment Start Date
 
Note that the oral lead-in period is only applicable to the participants who received at least one dose of study treatment during the oral lead-in period in the study. Oral lead-in period is within the maintenance phase.

NOTES:

- Date = AE Start date.

Table 19 Assignment of Study Period for Lab Assessments:

Period	Date range
Oral Lead-in	
For participants receiving at least one Injection: Maintenance Treatment Start Date < Date \leq Date of First IM Injection
 
For participants withdrawing prior to first Injection: Date > Maintenance Treatment Start Date
 
Note that the oral lead-in period is only applicable to the participants who received at least one dose of study treatment during the oral lead-in period in the study. Oral lead-in period is within the maintenance phase.

NOTES:

- Date = Date of assessment.

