6.38	NA	NA	Q4W ATLAS	Shell HO_T1	Proportion of Subjects with Response to Each Individual Question in Preference Questionnaire at Week 48 (Maintenance Phase) for Subjects from Q4W ATLAS to Q8W ATLAS-2M	Only display Q8W arm.	HL, W48
6.39	NA	NA	Intent-to-Treat Exposed	Shell HO_T1	Proportion of Subjects with Response to Each Individual Question in Preference Questionnaire by Prior Exposure to CAB+RPV (0 vs. >=1 Weeks) at Week 48 for Subjects in Q8W ATLAS-2M (Maintenance Phase)	Only display Q8W arm.	W48
6.40	NA	NA	Intent-to-Treat Exposed	Shell HO_T1	Proportion of Subjects with Response to Each Individual Question in Preference Questionnaire at Week 48 for Subjects in Q4W ATLAS-2M (Maintenance Phase)	Only display Q4W arm.	W48
Reasons for Switch/Continuation							
6.41	NA	NA	SOC	201585/primary_02/T7.40	Reasons for Switch at Baseline for Subjects from SOC	Remove columns 'Analysis Visit' and 'Total'. For percentages, use the format 'xx / xx (xx%)' where the denominator is the number of subjects with available valid data from the questionnaire.	W48

Health Outcomes Tables							
No. in W48	No. in W96	No. in EOS	Population	IDSL / Example Shell	Title	Programming Notes	Deliverable
6.42	NA	NA	Q4W ATLAS	201585/primary_02/T7.40	Reasons for Continuation at Baseline for Subjects from Q4W ATLAS	Remove columns 'Analysis Visit' and 'Total'. For percentages, use the format 'xx / xx (xx%)' where the denominator is the number of subjects with available valid data from the questionnaire.	W48

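### Table 6.39 counts Q8W-arm participants who stop during oral lead-in, although the Preference form tells them not to choose the 8-week answer

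*SAP*

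**What the plan says.** **The item.** In SAP section 15.6.6 the first Preference question asks which HIV treatment the respondent prefers, judged from experience. It offers four answers: injections every 4 weeks, injections every 8 weeks, daily oral treatment, no preference. Only the 8-week answer carries a condition: "only select this answer if you received the 8-week injectable regimen of CAB LA + RPV LA during study".

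**Who completes it, and when.** The footnotes to the Q8W schedule (section 15.2.2) say "Preference Questionnaire will be administered to all participants" and, for early stoppers, "Conduct questionnaires/surveys upon Withdrawal only if occurring at or prior to Week 48". The endpoint in section 2.2 is likewise set at Week 48 or withdrawal.

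**Where a withdrawal response goes.** Section 15.3.4.1 tests study phase only: "Proceed to step b if the assessment is assigned to the Maintenance Phase". With no earlier planned record, "then the unscheduled/withdrawal visit will be slot to the first planned nominal visit after Day 1". Table 12 plans Preference at Week 48 and nowhere else. Section 15.4.3 adds: "Oral lead-in period is within the maintenance phase".

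**Who is counted.** ITT-E in section 4 is defined as "All randomized subjects who received at least one dose of study treatment". Section 15.6.1 accepts an oral dose as the start of treatment, and section 5.1 reports the sequence of oral treatment followed by Q8W under Q8W. Table 6.39 (section 15.14.5.10) uses ITT-E, shows the Q8W arm only and splits by prior exposure (0 versus at least 1 week). Its title includes "at Week 48 for Subjects in Q8W ATLAS-2M (Maintenance Phase"). Table 6.40 is the Q4W counterpart, also on ITT-E.

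**Data handling for Preference.** Section 15.6.6 says only that missing values are not imputed.

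**The concern.** Only participants coming from oral therapy take the oral lead-in. If one of them is randomised to Q8W, withdraws before the first injection and completes the form, the response is a structural zero for Q8W preference: it sits in the denominator and, by instruction, not in the numerator. The same person in the Q4W arm meets no such condition and may tick the 4-week answer without ever having had an injection. Neither response reflects experience of an injectable regimen, which is what the item asks about.

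Preference for each injectable regimen over oral therapy, and for Q8W over Q4W, are secondary objectives (section 2.2). The neighbouring instruments in section 15.6.6 have rules on which responses are valid: HIVTSQc by questionnaire version, Reasons for Switch/Continuation by version and timing. Preference has none, so the gap looks like an oversight. At stake is how the 0-week stratum of Table 6.39 is read: part of any shortfall in Q8W preference there would come from the form's wording and not from participants' experience.

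**Working it through.** The SAP states no preference rate, no count of lead-in withdrawals and no number of responders, so there is no plan figure to reproduce. The check has two parts.

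**1. Following one participant through the rules.** Take a participant from oral therapy, randomised to Q8W, who takes oral lead-in tablets, withdraws before Week 4B and completes the form.

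- *Phase.* Section 15.6.1 leaves the long-term follow-up treatment start date missing for someone who discontinued without any injection. The note to Table 14 then applies the lower bound only, so the withdrawal visit stays in the Maintenance Phase.
- *Visit.* No planned Preference record exists before Week 48, so the fallback in section 15.3.4.1 applies and the response becomes Week 48.
- *Population and column.* ITT-E, Q8W.
- *Display.* Table 6.39, 0-week stratum.
- *Possible rescue by treatment state.* Under Table 16 a visit more than one day after the last oral dose is post-treatment. But the on-treatment condition in section 15.3.1 governs the Maintenance Phase windows for data other than health outcomes and PK, and the on-treatment wording in section 15.3.6 only chooses between several records at one visit. Neither clearly removes a single Preference record.
- *Denominator.* The programming notes for Tables 6.38 to 6.40 do not state one, and the shell is not part of the document. If it is responders, lead-in withdrawers who completed the form count. If it is all of ITT-E, every lead-in withdrawer counts. These people are included either way.

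**2. Size.** Let n be the responders in the affected stratum, w those never injected, and p the share of the other n − w who prefer Q8W.

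- Observed share = p(n − w)/n
- Understatement = p − p(n − w)/n = pw/n
- Highest attainable share = (n − w)/n

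All inputs are assumptions. With n = 330 and p = 0.90, rounding to whole people:

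| w | Injected only | With never-injected | Difference (points) | Highest attainable |
|---|---|---|---|---|
| 3 | 294/327 = 89.9% | 294/330 = 89.1% | 0.8 | 327/330 = 99.1% |
| 5 | 292/325 = 89.8% | 292/330 = 88.5% | 1.4 | 325/330 = 98.5% |
| 10 | 288/320 = 90.0% | 288/330 = 87.3% | 2.7 | 320/330 = 97.0% |

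Over a wider grid (n = 250, 330 or 510; w = 1 to 15; p = 0.80 to 0.98) the difference runs from 0.16 points (n = 510, w = 1, p = 0.80) to 5.9 points (n = 250, w = 15, p = 0.98). If the instruction is followed, the direction for Q8W is always downward.

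**The case against.** The strongest case against has five parts.

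*Withdrawal responses belong in the endpoint.* Section 2.2 counts them and section 12.3 bases health outcomes on ITT-E. Dropping people by what they received after randomisation changes the question being answered. This stands, and it is why the ITT-E row should be kept.

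*The scope is narrow.* Table 6.38, the only Preference display in the headline delivery, covers participants moving from Q4W in ATLAS to Q8W, who have no oral lead-in. Table 6.39 is already split by prior exposure, so its stratum with at least 1 week is clean. No Preference test appears in section 5.5.2 or 12.5.1, and lead-in withdrawals are listed (Listing 32). All of this stands.

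*The form instructs; it does not block.* It is a paper instrument, and someone could tick the 8-week box regardless. This stands, and the structural zero depends on the instruction being followed.

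*One injection is a weak test of experience.* In Q8W participants who had the lead-in, the Week 4B and Week 8 injections are 28 days apart (section 15.6.3), so one or two injections do not amount to a completed 8-week interval. This stands as a limit of the restricted row, which removes only the responses with no injection experience at all.

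*Section 15.7.1 lets withdrawal visits be slotted or summarised as withdrawal visits.* That is true in general, but section 15.3.4.1 is specific to these questionnaires and slots them.

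A reader might infer that the asymmetry also biases the comparison of injections with oral therapy. The documents do not support that: a never-injected Q8W participant may still tick the unrestricted 4-week answer and so count as preferring injections. Only the 8-week answer is affected.

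**Conclusion.** The point holds in a limited form. In the 0-week stratum of Table 6.39, and in any Q8W total that includes it, lead-in withdrawers who complete the form lower the reported Q8W preference without having had the regimen; no corresponding restriction applies to the 4-week answer in Table 6.40.

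The size is unknown. About 1 to 3 percentage points follows if roughly 330 people respond in the stratum, 3 to 10 of them were never injected, all follow the instruction, and 90% of the rest prefer Q8W. None of these values is in the SAP.

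A reader might go further and infer that Q8W preference is understated throughout the trial, or that the share preferring something other than an injection could more than double. The first fails because Table 6.38 and the stratum with at least 1 week of exposure contain no lead-in participants. The second needs an extreme assumed corner: 320 responders, a true share of 2%, and 10 never-injected people who all tick oral or no preference, giving (0.02 × 310 + 10)/320 = 5.1%. Nothing in the SAP supports those inputs. This is a cheap improvement to a descriptive secondary summary and does not threaten a trial conclusion.

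**What to change.** In section 15.6.6 (Preference, Data Handling) and in the programming notes for Tables 6.39 and 6.40:

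1. State the denominator as participants with a valid Preference response.
2. Keep the ITT-E row.
3. Add a row restricted to participants who received at least one CAB LA + RPV LA injection in ATLAS-2M before the assessment.
4. Show the responses of never-injected participants separately, so that nothing is hidden.
5. Say that the injected row is the one used to interpret preference based on experience.

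The cost is a sentence or two in the SAP, one extra summary row and the separate display of never-injected responses. The downside is a slightly smaller denominator in the restricted row, defined by exposure after randomisation. Because the ITT-E row stays beside it, the reader can see what the restriction changes.
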